#### B. Secondary Data Collection

Medical history, medications, clinical data related to and outcome of COVID-19-like illness (hospitalization or death) will be extracted from primary care and hospital medical records.

#### 1.10 Timetable/Schedule of Events

We expect to complete this trial within 10 months from contract execution. Detailed timeline is as follows:

	M1	M2	МЗ	M4	M5	M6	M7	M8	M9	M10
Institutional approval, staff training and material development						•			•	
Recruitment										
Intervention, sample measurement and clinical data collection										
Bioinformatics and data analysis										
Results dissemination										

# 2.2 Research Staff Training

All investigators have successfully completed the Collaborative Institutional Training Initiative (CITI) training.

#### 2.3 Resources Available

Castor, a cloud-based clinical data management platform, and its video call module eConsent, will be used for conducting preliminary screening surveys and virtual interviews for electronic informed consent and eligibility screening, compiling study data and tracking the progress of each participant and the overall study.

Study teams at USF, Rutgers University and Vault Health company will lead the screening, recruitment and enrollment efforts, which include identifying prospective participants, completing questionnaires and administering and/or coordinating tests to establish eligibility. The medical teams at USF and Rutgers University will monitor the clinical progress of participants in Florida and other states respectively, and provide medical support throughout the study, including a 24/7 on-call physician for medical questions related to COVID-19. ClinCard, a participant payment automation system at USF, will be used to provide a stipend for participation for those who are enrolled at the USF COVID testing center, which will be applied to the ClinCard within three working days after completing each specified milestone.

Protocol Title: COVGUT20

Vault Health is a digital healthcare company and a leading provider of COVID-19 testing and vaccination services in the United States. Vault's solutions have been deployed across 20 different industry segments, including energy, finance, aerospace, pharma/biotech, insurance, state government (e.g. Minnesota, New Jersey, Wyoming, Wisconsin and others), local municipalities, healthcare, recreation (e.g., summer camps), higher education (including athletic programs), and professional sports leagues. To date, Vault has provided COVID testing to over 2 million individuals, providing accurate and timely information in the battle against COVID. Vault is also providing state-sponsored vaccination services in New Jersey, Minnesota, Delaware and elsewhere around the United States. Vault maintains a clinical group practice of over 1,200 practitioners including physicians, advanced practice practitioners (NP / PA), nurses, and medical assistants with licenses spanning all 50 states. Since April of 2020, Vault has facilitated over 4.1 million tests across the United States for the presence of SARS-CoV-2 using the first FDA-authorized saliva-based test. Vault maintains a HIPAA-compliant database of all tests performed with patient information including name, date of birth, race, ethnicity, address / ZIP code, phone number, email address, symptoms of COVID-19 for each test taken, exposure to individuals suspected of or confirmed to have COVID-19 and time since exposure. Vault will utilize this database to identify individuals meeting the below inclusion/exclusion criteria across the United States and utilize "customer relationship management" (CRM) approaches to inform prospective candidates about the study and provide them an opportunity to participate if they meet inclusion criteria.

Fecal sample processing, next-generation sequencing, bioinformatics, and data analysis will take place at the Microbiome Core of New Jersey Institute for Food, Nutrition and Health at Rutgers University as a fee-for-service. Specifically, genomic DNA extraction will be extracted from fecal samples in a biosafety cabinet in a BSL-2 certified laboratory with enhancements. Isolated DNA will then be further processed (e.g. PCR, PCR product purification and dilution) for 16S rRNA V4 amplicon sequencing using the Ion GeneStudio S5 platform (ThermoFisher Scientific). Sequencing data will be analyzed using the Rutgers University high-performance computing cluster Amarel. The Microbiome Core owns a 2X Intel Xeon Skylake 6130 Node (22M Cache, 2.666 MHz, 192 GB RAM, 5 TB storage) of the high-performance computing cluster, which provides the research team high priority and guaranteed access.

# 3.0 Multi-Center Research

The conduct of the current protocol will be carried out at University of South Florida and Rutgers University.

#### 4.0 Subject Considerations

Protocol Title: COVGUT20

#### 4.1 Subject Selection and Enrollment Considerations

#### A. Method to Identify Potential Subjects

For recruitment at the USF COVID testing center and Rutgers University medical schools, testing schedules at the USF Carol & Frank Morsani Center for Advanced Healthcare drive-through testing center and testing center at Rutgers University medical schools will be screened to identify potential study candidates. Family physicians will be contacted, and flyers will be used to increase advertising exposure. Individuals who call the COVID-19 hotline will also be informed about the study. For online recruitment, Google, Facebook and Twitter advertisements will be sent to residents of mainland US. A link to the landing page of the study will also be distributed to family physicians and doctors in the USF and Rutgers University medical schools and facilities via email, text or messaging apps for them to share with their patients and networks. For recruitment from Vault Health company, individuals who has COVID-19 related symptoms and has been tested positive for COVID-19 using service from Vault Health company will be contacted by Vault Health. An email containing a brief description of the study and a link to the landing page will be sent to the potential participants.

#### **B.** Recruitment Details

## Recruitment at the USF COVID testing center and Rutgers University medical schools:

- Drive-through testing center. Individuals who have scheduled an appointment at the testing center will be pre-screened. Those appear to be eligible for this study will be contacted by a study coordinator.
- Referrals from family physicians: family physicians will be contacted by email (Appendix 13) about this study and provided with recruitment contacts.
- Flyers: flyers (Appendix 14) will be posted on the USF campuses, clinics, neighborhoods nearby and social media. Flyers will also be distributed to USF faculties, staff and students via mailing lists.
- COVID-19 hotline: individuals who call the COVID-19 hotline will be provided information about this study and contact details of the research team.

#### Online recruitment:

Individuals who are interested in participating in the study will access the landing page of the study (Appendix 19) either via the Google/Facebook/Twitter advertisements (Appendix 20) or the link shared by their family physicians, USF or Rutgers University. They will register and complete an online self-administered preliminary screening survey. Those appear to be eligible will proceed to an informed consent interview and further screening.

## Recruitment from Vault Health company:

Individuals who has COVID-19 related symptoms and has been tested positive for COVID-19 using service from Vault Health company will be contacted by Vault Health. An email containing a brief description of the study and a link to the landing page will be sent to the potential participants. If the study candidate is interested in the study, they will register and complete an online self-administered preliminary screening survey. Those appear to be eligible will proceed to an informed consent interview and further screening.

# C. Subject Screening

# Inclusion Criteria

- Aged between 18 to 79 (inclusive)
- Have mild to moderate COVID-19-like symptoms based on the symptom list from CDC (updated May 13, 2020) and the severity categorization from FDA [18]:
  - a) Mild COVID-19

- Fever or chills, cough, shortness of breath or difficulty breathing, fatigue, muscle or body aches, headache, new loss of taste or smell, sore throat, congestion or runny nose, nausea or vomiting, and diarrhea
- · No clinical signs indicative of moderate, severe, or critical illness severity
- b) Moderate COVID-19
  - Symptoms of moderate illness with COVID-19 could include any symptom of mild illness or shortness of breath with exertion
  - Clinical signs suggestive of moderate illness with COVID-19, such as respiratory rate ≥ 20 breaths/min, oxygen saturation level > 93% on room air at sea level, heart rate ≥ 90 beats/min
  - No clinical signs indicative of severe or critical illness severity.
- Directed to home isolation by study physician

\_

- Practice acceptable contraception, i.e., continue with current methods if participants are already
  practicing contraception, otherwise parti cipants must agree to practicing contraception with a
  barrier method (male or female condom) or abstinence, from Day 1 to Day 35 or 7 days after the
  last dose of NBT-NM108 if they do not complete the 28-day intervention.
- Have access to a smartphone, tablet, computer, or other qualifying internet-enabled device and daily internet access
- Understand and be able to follow written and oral instructions in English
- Provide informed consent

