INFORMED CONSENT AND ELIGIBILITY SCREENING PART 2. The informed consent process will be conducted via Castor's eConsent video call module. At the beginning of the call, the study coordinator will confirm that the study candidates continue to experience the COVID-19-like symptoms reported in the preliminary screening survey, thereafter the study coordinator will explain the rationale, aim, expected outcomes and significance of the research, the experimental procedures, what is required from the participants, and the benefits and risks associated with the study. Electronic informed consent will be obtained during the interview prior to further eligibility screening (Appendices 3 and 4). A consent for health information release (Appendix 3) will also be obtained during informed consent procedure. After the study candidates sign the electronic informed consent documents, the study coordinator will ask some additional questions regarding their medical history and other conditions to establish eligibility (Appendix 4). In the case of study candidates who are recruited online, they will also be asked to provide electronic proofs of a positive/pending COVID-19 test (Appendix 24) and a negative pregnancy test result (if appropriate; Appendix 6) during the interview. This consent and eligibility screening interview will take a maximum of 60 minutes to complete.

**ENROLLMENT.** The study physicians will review all screening data and determine if the study candidates are suitable for home isolation and confirm enrollment.

**RANDOMIZATION AND ALLOCATION CONCEALMENT.** Enrolled participants will be randomized to the control or treatment group at a 1:1 ratio, using randomization via a dynamic minimization to minimize imbalance between groups over factors including COVID-19-like illness severity (mild vs moderate), the use of COVID-19 vaccination or other treatments that may reduce severity such as monoclonal antibody treatment vs. not used, age (≤60 vs >60 years) and gender (male vs female) [16]. When imbalance is detected, the new patient will be allocated with probability 0.7 vs 0.3. When the treatment assignments are at balance, the patient will be allocated with probability 0.5 vs 0.5. The randomization will be performed

via a closed source app written by one of the Co-PI. The investigator who uses the app will only know the allocation result, i.e., control or treatment group, of the new patient.

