## D. Endpoints

- 1. Primary outcome:
  - Gut microbiota composition
- 2. Secondary outcomes:
  - At Days 1, 14, 28 and 56:
  - a) Outcome of COVID-19-like illness (hospitalization or death)
  - b) Proportion of participants who are "alive and not admitted to the hospital"
  - c) Proportion of participants who visit the emergency room
  - d) Proportion of participants who have complete resolution of all objective symptoms, i.e. all vital signs are within the normal range for at least 48 h, including body temperature (oral) 36.5-37.5°C (97.7-99.5°F), pulse rate 60-100/min, respiratory rate 12-20/min and oxygen saturation level at 95-100%
  - e) Proportion of participants who have complete resolution of subjective symptoms, i.e. absence of all COVID-19-like symptoms listed by CDC (updated May 13, 2020) for at least 48 h, including the presence of chills or "feeling feverish", cough, shortness of breath or difficulty breathing, fatigue, muscle or body aches, headache, new loss of taste or smell, sore throat, congestion or runny nose, nausea or vomiting and diarrhea
  - f) Proportion of participants who have complete resolution of subjective symptoms except fatigue and cough, i.e. absence of all COVID-19-like symptoms listed by CDC (updated May 13, 2020) for at least 48 h, including the presence of chills or "feeling feverish", cough, shortness of breath or difficulty breathing, fatigue, muscle or body aches, headache, new loss of taste or smell, sore throat, congestion or runny nose, nausea or vomiting and diarrhea
  - g) Illness severity based on the categorization from FDA [18] and the Ordinal Scale for Clinical Improvement from the World Health Organization [19]
  - h) Body temperature (oral)
  - i) Oxygen saturation level
  - i) Pulse rate
  - k) Respiratory rate
  - I) Fasting blood glucose
  - Time to complete resolution of all objective symptoms
  - Time to complete resolution of all subjective symptoms
  - Time to complete resolution of all subjective symptoms except fatigue and cough

Protocol Title: COVGUT20

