To monitor COVID-19-like symptoms, participants will evaluate their symptoms and report to the research team on Castor twice a day from Day 1 to Day 28 or until they recover from COVID-19-like illness (whichever is later) and once a week thereafter until Day 56 (i.e. the mornings of Days 35, 42, 49 and 56 as appropriate). For those who are hospitalized during the study, after they are discharged they will also be asked to evaluate their symptoms and report to the research team on Castor twice a day until they recover from COVID-19-like illness and once a week thereafter until Day 56. The study team will review the symptom diary within 24 h of each entry and follow up with the participants if the symptoms require medical attention. The study team will call all participants at least once a week to monitor their progress. Participants are also instructed to call 911 if they notice any of the following red flags: respiratory rate  $\geq$  30/min, pulse rate  $\geq$  125/min, oxygen saturation level  $\leq$  93%, severe shortness of breath at rest (inability to talk in full sentences), difficulty breathing, persistent pain/pressure in chest, cold/clammy/pale/mottled skin, new confusion or inability to wake up, blue lips or face, little or no urine output or hemoptysis. Participants with T2DM will be instructed to call the physician who normally manages their diabetes if their fasting blood glucose is < 60 mg/dL or > 300 mg/dL.

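### The mild/moderate rule cannot be applied as written: normal oxygen saturation counts as a sign of moderate illness, and mild allows no such sign

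*Protocol*

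**What the plan says.** The relevant text stands in four protocol sections and in the analysis text.

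- **Protocol 4.1 C, Inclusion Criteria.** The categories are attributed to "the severity categorization from FDA [18"]. Moderate illness is described by signs that are called suggestive and introduced as examples: a respiratory rate of 20 or more, "oxygen saturation level > 93% on room air at sea level" and a heart rate of 90 or more. The category is subject to "No clinical signs indicative of severe or critical illness severity". Mild illness requires "No clinical signs indicative of moderate, severe, or critical illness severity".
- **Protocol 1.3 D, Endpoints.** Item (d), resolution of objective symptoms, takes as normal a pulse of 60-100/min together with "respiratory rate 12-20/min and oxygen saturation level at 95-100"%. Item (g) is illness severity by the FDA categories and the WHO ordinal scale. Both items are assessed at Days 1, 14, 28 and 56.
- **Protocol 4.7 E, Minimizing Risks of Harm.** "Participants are also instructed to call 911 if they notice any of the following red flags"; the list includes saturation of 93% or below, respiratory rate of 30 or more and pulse of 125 or more.
- **Protocol 1.3 A, Randomization.** One of four minimization factors is "COVID-19-like illness severity (mild vs moderate").
- **Protocol 6.1 and SAP, Clinical Data Analysis.** Baseline severity is named as a covariate for the Cox and Fine-Gray models. For the other analyses it is controlled only where the analyst finds it appropriate.

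**The concern.** The protocol's normal saturation range lies wholly inside the range it lists as a sign of moderate illness. Since mild illness excludes moderate signs, a participant with normal saturation cannot be mild under the text.

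The category does real work in this trial. It is meant to balance the arms, and baseline severity is meant to adjust the time-to-event models. A minimization factor with one level balances nothing, and a one-level covariate cannot be estimated. If some staff apply the text literally and others do not, the factor would depend on who classified the participant. Nothing in the documents shows that this has happened.

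**Working it through.** The documents give no expected mild/moderate split, so there is no stated figure to reproduce. The check is on the logic, followed by a simulation of what a collapse would cost.

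**1. The three vital signs side by side**

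| | Sign of moderate illness (4.1 C) | Normal (1.3 D, item d) | Red flag (4.7 E) |
|---|---|---|---|
| Oxygen saturation | > 93% | 95-100% | ≤ 93% |
| Respiratory rate | ≥ 20/min | 12-20/min | ≥ 30/min |
| Heart or pulse rate | ≥ 90/min | 60-100/min | ≥ 125/min |

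**2. Literal reading.** Mild requires saturation ≤ 93%, respiratory rate < 20 and heart rate < 90. Having no red flag requires saturation > 93%. The two conditions exclude each other, so the mild class is empty among people without a red-flag saturation.

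The same can be counted over whole-number combinations with no vital-sign red flag: saturation 94-100 (7 values), respiratory rate 10-29 (20) and heart rate 50-124 (75). The lower ends, 10 and 50, are chosen for the count.

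- Total: 7 × 20 × 75 = 10,500 combinations, of which 0 are mild and 10,500 moderate.
- Within the protocol's own normal ranges: 6 × 9 × 41 = 2,214 combinations, all moderate.

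**3. Boundary reading.** Here > 93% only separates moderate illness from the red-flag range. Moderate then means respiratory rate ≥ 20 or heart rate ≥ 90. The plan does not say how the signs combine; one is taken as enough.

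- Mild: 7 × 10 × 40 = 2,800. Moderate: 10,500 − 2,800 = 7,700. Both levels exist.
- Within the normal ranges, mild: 6 × 8 × 30 = 1,440. Moderate: 2,214 − 1,440 = 774, or 774/2,214 = 35%.

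The 774 arise because respiratory rate 20 and heart rate 90-100 sit in both lists. All of these are counts of combinations, not patient frequencies.

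**4. Cost of a collapse.** Minimization was simulated with N = 100, four two-level factors, equally weighted signed differences summed over factors, allocation 0.7/0.3 under imbalance and 0.5/0.5 at balance, and 3,000 runs. N, the number of factors and the probabilities are the protocol's. The imbalance measure, a true moderate share of 20-50% and prevalences of 30%, 20% and 50% for the other factors are assumptions. The outcome is the absolute difference between arms in the number of truly moderate patients.

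| True moderate share | Severity at two levels: mean (95th percentile) | Severity at one level: mean (95th percentile) |
|---|---|---|
| 20% | 1.8 (5) | 3.3 (8) |
| 35% | 1.9 (5) | 3.8 (9) |
| 50% | 1.9 (5) | 4.1 (10) |

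**The case against.** The best reply is that nobody would apply the text literally. The signs are called suggestive and are introduced as examples. The red flag at 93% or below is the exact complement of the moderate sign, and a two-level factor presupposes that both levels are filled. Together these favour reading > 93% as the limit against severe illness. Study physicians also review the screening data before enrollment. This stands as an account of what was probably meant, but it does not supply a rule: the text neither assigns that role to the figure nor says how the signs combine. The physicians' review is described as deciding suitability for home isolation and confirming enrollment, not as setting the severity level.

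A second reply is that endpoint (d) serves follow-up while the inclusion criteria serve screening, so overlapping ranges do no harm. That holds only in part. Item (g) applies the FDA categories on the same days as item (d), so one participant could count as resolved and as having signs of moderate illness at one visit. It is true that the longitudinal severity analysis uses the WHO scale and that no analysis is specified for the FDA category.

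A reader might infer more: that hardly anyone was classed as mild, that minimization ran on three factors instead of four, and that severity dropped out of every clinical model. The documents do not support this.

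- The study oximeter is shipped upon enrollment and randomization, so a study-device saturation would not be available when the minimization level is set.
- The screening surveys, the checklist and the app's severity rule are not in these documents and may contain a working definition.
- Baseline severity is not defined as the FDA category, and Day 1 severity is assessed on two scales.
- The log-rank and Gray's tests take no covariates, and only the Cox and Fine-Gray models name severity explicitly.

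**Conclusion.** The mild/moderate rule is wrong as written. Literally, it leaves no mild participants without a red-flag saturation, while the protocol minimizes on mild versus moderate. Collapse of the factor, and of the covariate if it uses the same categories, is a consequence of the literal text and has not been shown to occur.

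The practical effect is limited. Under the stated assumptions, a full collapse would raise the mean arm difference among moderate patients from 1.8-1.9 to 3.3-4.1, and its 95th percentile from 5 to 8-10. Allocation would remain random, and the PERMANOVA for the primary outcome names no severity adjustment. The overlap at respiratory rate 20 and heart rate 90-100 persists on either reading. The FDA source was not available, so whether the protocol reproduces it faithfully is left open.

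**What to change.** - Reconcile Protocol 1.3 A (Randomization), 1.3 D (Endpoints), 4.1 C (Inclusion Criteria) and 4.7 E (Minimizing Risks of Harm).
- State whether saturation > 93% is the limit against severe illness or a sign that makes a case moderate, and how the listed signs combine.
- Resolve or explain the values that are both normal in endpoint (d) and signs of moderate illness.
- Use one mutually exclusive mild/moderate rule, the same at all sites and in the randomization app, for the minimization factor and the baseline-severity covariate. Say in the SAP that the covariate is that category.

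The clinical thresholds are for the investigators to settle; none is proposed here. The cost is wording in the protocol and SAP and a check of the app's severity rule. Sample size and data collection do not change.
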